EC ₅₀	Half maximal effective concentration						
ECMO	Extracorporeal membrane oxygenation						
eCRF	Electronic case report form						
EDC	Electronic data capture						
FDA	Food and Drug Administration						
FiO2	Fraction of inspired oxygen						
FPHU	FUJIFILM Pharmaceuticals U.S.A., Inc.						
GCP	Good Clinical Practice						
HIV	Human immunodeficiency virus						
IB	Investigator Brochure						
ICH	International Conference on Harmonization						
IEC	Institutional ethics committee						
IRB	Institutional review board						
ITT	Intent-to-treat						
IUD	Intra-uterine device						
MedDRA	Medical dictionary for regulatory activities						
MERS-CoV	Middle East respiratory syndrome coronavirus						
MITT	Modified intent-to-treat						
NEWS2	National early warning score 2						

NO	Nitrous Oxide						
PaO2	Partial pressure of oxygen						
PCR	Polymerase chain reaction						
PI	Principal Investigator						
PK	Pharmacokinetic(s)						
PP	Per-protocol						
RNA	Ribo-nucleic acid						
RT-PCR	Reverse transcriptase polymerase chain reaction						
SAE	Serious adverse event						
SARS-CoV-2	Severe acute respiratory syndrome corona virus 2						
SD	Standard deviation						
SOC	Standard of care						
SpO2	Peripheral capillary oxygen saturation						
SUSAR	Suspected unexpected serious adverse reaction						
TCID ₅₀	Median tissue culture infectious dose						
TEAE	Treatment-emergent adverse event						
TTCR	Time to clinical recovery						
WHO	World Health Organization						

1 SYNOPSIS

Title	Open Label, Randomized, Controlled, Phase 2 Proof-of-Concept Study of the Use of Favipiravir v. Standard of Care in Hospitalized Subjects with COVID-19
Design	This is an open label, randomized, controlled, multicenter Phase 2 proof-of-concept study of favipiravir in hospitalized subjects with COVID-19. Subjects will be randomized within their study site and stratified by the severity of their disease to receive either favipiravir + standard of care (SOC) or SOC alone.
	The dose regimen will be 1800 mg favipiravir BID plus SOC or SOC alone on Day 1 followed by 1000 mg BID favipiravir (800 mg BID for subjects with Child-Pugh A liver impairment) plus SOC or SOC for the next 13 days.
	The study will have 14 days of treatment and 46 days of follow-up.
Objectives	Primary Objective
	To determine the effect of favipiravir + SOC v. SOC on viral clearance.
	Secondary Objectives
	 To determine the clinical benefit of administering favipiravir plus SOC compared to SOC alone [assessed using a study-specific 6-point ordinal scale adapted from the WHO Master Protocol (V2.0 24FEB20) COVID-19 7-point ordinal scale] on Day 15 in adult patients hospitalized with COVID-19. To determine if the treatment effect on the 6-point ordinal scale, on Day 15, is reasonably likely to reflect clinical benefit, such that it can be used as the primary clinical outcome endpoint in a similar study that is double-blinded, by assessment of the relationship of the scale to changes in clinical and symptom outcomes, including time to clinical recovery, occurrence of fever, cough, dyspnea, reduction in oxygen requirements, and other measures. To explore the clinical effect of favipiravir + SOC v. SOC as measured by the National Early Warning Score 2 (NEWS2) system. To determine the safety of favipiravir plus SOC compared to SOC alone, in this population. To explore the PK of this dose regimen of favipiravir in this patient population.
Endpoints	Primary Endpoint:
	Time to viral clearance.
	Secondary Endpoints:
	1. Status of Clinical recovery as measured by the study-specific 6-point ordinal scale at Day 15.

- 2. Time to Clinical Recovery (TTCR) as assessed up to 29 days and defined as:
 - a. The time (in hours) from initiation of study treatment (favipiravir + SOC or SOC alone) until normalization of fever, respiratory rate, and oxygen saturation, and alleviation of cough, sustained for at least 72 hours; or discharge.
 - b. Normalization and alleviation criteria are defined as:
 - i. Fever ≤ 37.2 °C oral,
 - ii. Respiratory rate ≤ 24 /minute on room air,
 - iii. Oxygen saturation SpO2 > 94% on room air,
 - iv. Cough mild or absent on a patient reported scale of severe, moderate, mild, absent.
- 3. Clinical effect as measured by the National Early Warning Score 2 (NEWS2) system.
- 4. All-cause mortality as assessed daily up to 29 days and at final follow up on Day 60.
- 5. Frequency of respiratory progression as assessed up to 29 days (daily and per SOC at each site) and defined as:
 - a. SpO2 \leq 94% on room air or PaO2/FiO2 \leq 300mmHg, and
 - b. requirement for supplemental oxygen, or
 - c. more advanced ventilator support.
- 6. Time to defervescence (in those with fever at enrollment) as assessed daily up to 29 days and at Day 60 (if possible).
- 7. Time to cough reported as mild or absent (in those with cough at enrollment rated severe or moderate) as assessed daily up to 29 days and on Day 60.
- 8. Time to dyspnea reported as mild or absent (on a scale of severe, moderate, mild absent, in those with dyspnea at enrollment rated as severe or moderate) as assessed daily up to 29 days and on Day 60 (if possible).
- 9. Frequency of requirement for supplemental oxygen or non-invasive ventilation as assessed daily up to 29 days and on Day 60.
- 10. Time to SARS-CoV-2 RT-PCR negative in upper respiratory tract specimen as assessed up to 29 days.
- 11. Change in SARS-CoV-2 viral load in upper respiratory tract specimen as assessed by area under viral load curve as assessed up to 29 days.
- 12. Frequency of requirement for mechanical ventilation as assessed up daily to 29 days and at Day 60
- 13. Safety of favipiravir + SOC v. SOC alone as assessed daily up to 29 days and at Day 60.
- 14. C-reactive protein (CRP) over time.
- 15. Population PK analysis of favipiravir with assessment of maximum plasma concentration (C_{max}), minimum plasma concentration (C_{min}), and AUC_(0-24h) on Days 1, 2, 8 and 14.

Study Sites	Approximately 8 sites in the U.S.A.
Planned Enrollment	Approximately 50 subjects; randomized 1:1
Study Population	Adults who are hospitalized for treatment of confirmed COVID-19
	 Adults who are hospitalized for treatment of confirmed COVID-19 Inclusion Criteria (all questions must be answered YES) 1. Adults (18 to 80 years old): a. within 72 hours of their hospitalization for infection with SARS-CoV-2, AND, b. within 72 hours of the latest PCR positive result and within 7 days of the 1st PCR positive result for SARS-CoV-2. (The latest PCR could be the only PCR result.), AND, c. within 10 days of onset of any COVID-19 symptoms. 2. Subject or their legal representative understands the requirements of the study and provides written informed consent prior to undergoing any treatment-related procedures. 3. If male, subject must: a. Be sterile (e.g., have had a vasectomy at least 6 months prior to Day 1 dosing), OR, b. Agree not to donate sperm during the study and for seven days following the last dose of study medication, AND, c. Agree to strictly adhere to the following contraceptive measures during the study and for seven days following the last dose of study medication: i. Abstain from sexual intercourse. ii. Use a condom during sexual intercourse with a female of child-bearing potential. In addition, the female partner must use another form of contraception (e.g. intrauterine device [IUD], diaphragm with spermicide, oral contraceptives, injectable progesterone, or subdermal implants). 4. If female, subject must: a. Be unable to bear children (have not had a period for ≥ 12 consecutive months, have had her uterus or ovaries removed, or have had a tubal ligation), OR, b. Must ensure that their male partner is incapable of fathering a child (e.g., has had a vasectomy at least 6 months prior to study entry), OR, c. If she is of childbearing potential will strictly adhere to the following contraceptive measures during the study and for seven days following the last dose of study medication:
	 i. Abstain from sexual intercourse, OR, ii. Must ensure that her male partner agrees to use a condom during sexual intercourse and agree to use an

approved method of contraception (e.g., IUD, diaphragm with spermicide, oral contraceptives, injectable progesterone, or subdermal implants).

- d. Agrees to stop breast-feeding prior to first dose of study drug and through seven days after completing therapy.
- e. Has a negative pregnancy test at screening.
- f. Has not had unprotected sexual intercourse within the past month.

Exclusion Criteria (all questions must be answered NO)

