- AST or ALT $> 8 \times ULN$
- ALT or AST $> 3 \times ULN$ AND total bilirubin $> 2 \times ULN$
- AST or ALT > 3 × ULN AND patient has right upper quadrant pain or eosinophilia
- Uric acid > 20 mg/dL

Study Measurements: Efficacy, Safety and PK

Primary Efficacy Measurement:

Presence of virus in the nasopharyngeal and oropharyngeal samples taken on Days 1, 3, 8, 11, 15 and 29 (if hospitalized and when able to return to clinic after discharge). Swabs will also be obtained on day of discharge from hospital if discharge occurs before Day 15.

Secondary Measurements (Efficacy, Safety and PK):

- 1. Clinical improvement of hospitalized subjects with COVID-19 receiving either favipiravir + SOC or SOC alone as defined by the following study-specific 6-point ordinal scale at Day 15
 - a. Not hospitalized
 - b. Hospitalized, not requiring supplemental oxygen
 - c. Hospitalized, requiring supplemental oxygen
 - d. Hospitalized, on non-invasive ventilation or high flow oxygen devices
 - e. Hospitalized, on invasive mechanical ventilation or ECMO
 - f Death
- 2. Status on the 6-point ordinal scale assessed daily while hospitalized and at each outpatient visit until Day 60.
- 3. NEWS2 assessed daily while hospitalized and at each outpatient visit until Day 60.

- 4. Patient status assessed daily while hospitalized and at each outpatient visit until Day 60 via Study-specific Symptom Status and the ECOG Performance Status questionnaires (see Appendix A).
- 5. Duration of supplemental oxygen (if applicable).
- 6. Duration of mechanical ventilation (if applicable).
- 7. Duration of hospitalization.
- 8. Date and cause of death (if applicable).
- 9. Safety as assessed by:
 - a. Observed and reported adverse events.
 - b. Hematology and chemistry laboratories on Days 1; 3, 8, 11, 15 and 29 (if hospitalized and when able to return to clinic after discharge)
 - c. Physical Examination at screening, Day 15 and Day 29.
 - d. Vital signs daily while hospitalized and at each outpatient visit until Day 60
- 10. Qualitative and quantitative PCR and TCID50 in nasopharyngeal and oropharyngeal swabs on Days 1 (pre-dose); 3, 8, 11, 15 and 29 (if hospitalized and when able to return to clinic after discharge). Swabs will also be obtained on day of discharge from hospital if discharge occurs before Day 15.
- 11. Blood for determination of antibodies to SARS-CoV-2 will be obtained on Days 1, 15 and 29 (if hospitalized and when able to return to clinic after discharge).

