8.4 Safety Assessments

Abnormal clinical laboratory values that are clinically significant and all reported adverse events will be graded according to the Common Terminology Criteria for Adverse Events (CTCAE) version 5.0.

Safety will be assessed by the collection of observed and reported adverse events, physical exams, vital signs, and the following clinical laboratory tests:

Hematology

Hemoglobin (Hgb) Hematocrit (Hct)
Platelet count Red blood cell count

White blood cell count with differential

Chemistry

Blood Urea Nitrogen (BUN) Creatinine

Total bilirubin Alkaline Phosphatase

Aspartate transaminase (AST)

Gamma-glutamyl transferase (GGT)

Alanine transaminase (ALT)

Lactic dehydrogenase (LDH)

Glucose Albumin
Total protein Bicarbonate
Phosphate Sodium
Potassium Chloride

Calcium Total cholesterol
Urate C-reactive protein

D-dimer

NOTES:

• All clinical laboratory assessments listed above (hematology and chemistry) will be conducted at each site's local clinical laboratory.

• If coagulation assays are ordered as part of the SOC, the results should be added to the EDC.

Including PK and Clinical Laboratory Testing, subjects will undergo 9 planned venipunctures during this study.

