9.6 Efficacy Endpoint Analysis

The primary endpoint of time to viral clearance will be analyzed with the log-rank test for treatment difference and summarized using the Kaplan-Meier methodology as noted above. Viral load results from day of discharge as available will also be included in the analysis of viral clearance.

The key secondary endpoint of status of clinical recovery as measured by the study-specific 6-point ordinal scale at Day 15 will be analyzed using ordinal categorical data methods, since it is unlikely that linear differences exist between the elements of the scale (for example, a 1-point difference in magnitude may not apply to each increment on the scale). As an exploratory analysis, sequential binary analysis will be performed, based on successive classification of a subject into categories of less than or greater/equal to each ordinal item on the scale. Longitudinal analysis of the 6-point scale over time on study will also be performed to investigate temporal patterns of improvement.

Time to event endpoints will be analyzed using similar methods as used for the primary endpoint; these will include time to: clinical recovery; defervescence; cough mild or absent; dyspnea mild or absent; SARS-CoV-2 RT-PCR negative in upper respiratory tract.

Categorical endpoints will be analyzed using categorical data analysis methods; continuous data will be analyzed using analysis of variance with treatment and strata as factors.

Missing efficacy data in a trial of hospitalized patients is generally unlikely, and great care will be taken at each study site to ensure that all outcome assessments are obtained as planned in this protocol. However, as treatment of COVID-19 subjects evolves, it is clear some subjects will be discharged from the hospital prior to Day 15. Subjects are asked to return for follow up visits on Days 29, 45 and 60. This requirement is presenting challenges for subjects and in order to ensure that in cases where the subject does not return for their follow up visits, an additional swabbing has been added on the day of hospital discharge (See Section 7.7). Should missing data occur for the primary endpoint, time to viral clearance, such patients will be included in the log-rank analysis as censored observations. Missing clinical outcome data will be evaluated using a variety of methods, including multiple imputation, worst-value assignment, and other methods, to be completely outlined in the statistical analysis plan.

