### 1.2.6.3. Safety Parameters

Abnormal clinical laboratory values that are clinically significant and all reported adverse events (AEs) will be graded according to the Common Terminology Criteria for Adverse Events (CTCAE) version 5.0.

Safety will be assessed by the following:

- Observed and reported AEs (including solicited and unsolicited events)
- Hematology and chemistry laboratories on Days 1, 3, 5, 8, 11, 15 and 29; if coagulation laboratory assays are ordered as part of the SOC, the results will be recorded
- Limited physical examination assessed daily while hospitalized and at each outpatient visit until Day 60.

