#### 4.5.3. Laboratory Data

Clinical laboratory values will be expressed in SI units.

All laboratory data will be provided in data listings.

Abnormal clinical laboratory values that are clinically significant will be graded according to the CTCAE version 5.0. A listing of all abnormal laboratory values will be provided.

Shift tables for hematology and chemistry parameters from baseline to worst value will be provided by treatment group and overall. All unscheduled visits, if any, will contribute to the last or worst value.

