## **5. CHANGES TO PLANNED ANALYSES**

The following are changes between the protocol-defined statistical analyses and those presented in this statistical analysis plan:

- The hierarchical testing of the key secondary endpoints has been removed, given that this study is a Proof of Concept study that is not meant to act as a pivotal or confirmatory study for marketing authorization.

All changes from procedures outlined in the protocol and procedures outlined in this SAP will be summarized in the study report. Decisions to deviate from planned analyses will be documented at the time they are made.

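### Secondary endpoint 14 (CRP over time) has no analysis in the SAP, and the baseline-to-worst shift table that covers CRP shows no time course and hides most declines

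*Protocol*

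**What the plan says.** **Protocol.** The synopsis lists "C-reactive protein (CRP) over time" as secondary endpoint 14, with no metric, time point or method. CRP belongs to the local-laboratory chemistry panel in section 8.4, and the synopsis sets the sampling as "Hematology and chemistry laboratories on Days 1; 3, 8, 11, 15 and 29". Two general provisions could apply to it. Section 9.6, on efficacy endpoints, says "continuous data will be analyzed using analysis of variance with treatment and strata as factors". Section 9.7, on safety, plans summaries of laboratory changes over time and counts of low, normal and high values, by treatment at each visit.

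**SAP.** CRP is not named in the efficacy parameters (1.2.6.1), in any secondary efficacy analysis (4.3.2.1 to 4.3.2.10) or in the laboratory section (4.5.3). As a chemistry parameter it falls under 4.5.3, which gives subject listings and one by-arm output: "Shift tables for hematology and chemistry parameters from baseline to worst value will be provided by treatment group and overall". The same section adds "All unscheduled visits, if any, will contribute to the last or worst value", but defines no baseline-to-last table and does not say whether *worst* can be the baseline value. Section 5 lists a single departure from the protocol: "The hierarchical testing of the key secondary endpoints has been removed".

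**The concern.** A numbered secondary endpoint that asks about a course over time is left with a display that has no time axis. The hoped-for movement in CRP is downward, while a worst-value table is built to pick up upward movement. Followed as written, the SAP gives neither a CRP profile by arm nor a between-arm estimate.

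The stake is moderate but real. The trial is open label, and clinical recovery can be met by discharge or depends partly on patient-reported cough. CRP is laboratory-measured and is the only inflammatory marker among the endpoints. If scale, visits and model are not fixed in advance, any CRP result reported later will be post hoc.

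**Working it through.** The documents give no figure to reproduce for this endpoint. The check is a comparison of the texts, followed by two illustrations on stated assumptions.

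**1. Where each secondary endpoint is analysed in the SAP**

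| Protocol endpoint | SAP section |
|---|---|
| 1, 2, 3, 4 | 4.3.2.1, 4.3.2.2, 4.3.2.4, 4.3.2.7 |
| 5, 6, 7, 8 | 4.3.2.3.1 to 4.3.2.3.4 |
| 9, 12 | 4.3.2.5 |
| 10 | 4.3.1 (PCR, primary analysis) |
| 11 | 4.3.2.9 |
| 13 | 4.5 |
| 14 (CRP) | none |
| 15 | 4.4 |

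Endpoint 14 is the only one of the 15 without a section. ECOG status and neutralizing antibodies, which are not numbered endpoints, each have one (4.3.2.3.5 and 4.3.2.10). This looks like an oversight rather than a decision.

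**2. Laboratory summaries, side by side**

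- Protocol 9.7: changes over time, by treatment, at each visit.
- SAP 4.5.3: listings and a shift to the single worst value.
- SAP 4.5.4, for contrast: vital signs do get actual values and changes from baseline at each evaluation.

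The by-visit laboratory summary has dropped out, and Section 5 does not say so.

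**3. What a baseline-to-worst table shows when CRP falls**

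Assumptions, not from the documents: upper limit of normal 10 mg/L, shift categories relative to that limit, and a steady exponential fall from baseline B with halving time h days, so that CRP on day d = B × 2^(−(d−1)/h). Sampling is on Days 3, 8, 11, 15 and 29.

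*If worst includes baseline:* with a falling CRP the worst value is the baseline itself, so every subject who starts high reads High to High.

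*If worst means worst post-baseline:* with a falling CRP the worst value is the Day 3 value, and nothing after Day 3 affects the table. A fall shows only if B × 2^(−2/h) ≤ 10, that is B ≤ 10 × 2^(2/h):

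| h (days) | Largest baseline at which a fall shows (mg/L) |
|---|---|
| 1 | 40 |
| 2 | 20 |
| 4 | 14.1 |
| 6 | 12.6 |

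- B = 20, h = 1: Day 3 = 20 × 2^(−2) = 5.0. Reads High to Normal, so the fall shows.
- B = 100, h = 2: Day 3 = 50, Day 8 = 100 × 2^(−3.5) = 8.8, Day 15 = 100 × 2^(−7) = 0.8. Reads High to High, so the fall is hidden.

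Over baselines 15, 20, 50, 100 and 150 mg/L crossed with halving times 1, 2, 4 and 6 days, 16 of the 20 combinations read High to High, including every baseline of 50 or more. In all 20 the CRP is below 10 mg/L by Day 29.

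**4. What an ordinary analysis could give**

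Assumptions: log-scale residual SD 0.8 to 1.2 and complete data from 25 per arm (the planned 50 at 1:1). The 90% CI for the between-arm ratio is the estimate multiplied and divided by exp(1.677 × SD × √(2/25)):

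- SD 0.8: exp(1.677 × 0.8 × 0.283) = 1.46
- SD 1.2: exp(1.677 × 1.2 × 0.283) = 1.77

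An observed ratio of 0.5 would have an upper limit of 0.5 × 1.77 = 0.89 at the larger SD. With 15 per arm still contributing at a late visit and SD 1.2, the factor is exp(1.701 × 1.2 × √(2/15)) = 2.11, and the upper limit is 0.5 × 2.11 = 1.06, which no longer excludes 1.

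**The case against.** The best defence is that CRP is covered as a laboratory parameter. Protocol 8.1 does not list it among the efficacy assessments, no objective names it, and it sits between safety and PK in the endpoint list. Protocol 9.7 already plans a by-treatment, by-visit summary of laboratory changes, which nearly matches the endpoint's wording. SAP 3.3 promises descriptive tabulations for appropriate parameters, and SAP 3.11 sets visit windows for by-visit summaries. On this view the gap is one unspecified table for a late-listed endpoint in a proof-of-concept study, where SAP 3.2 makes every p-value except the primary one descriptive. A log-scale repeated-measures model would also go beyond the ANOVA in protocol 9.6.

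Much of this stands. Generic methods do exist in the protocol, a descriptive by-visit table would go a long way, and the choice between ANOVA and a repeated-measures model is open. It does not close the gap. Protocol 9.1 leaves the complete analysis details to the SAP, and SAP 1.1.2 makes its own analyses the basis for the study report and undertakes to set out differences from the protocol. SAP 3.3 names neither CRP nor a contrast between arms.

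Three stronger readings are tempting, and the documents support none of them:

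- *That the shift table cannot, by construction, show CRP falling.* This is true only if *worst* includes baseline, which SAP 4.5.3 does not say. On a post-baseline reading a small, fast fall can appear.
- *That the shift table is the only by-arm CRP summary planned anywhere.* It is the only one the SAP specifies; protocol 9.7 plans another.
- *That the endpoint cannot be answered.* Serial values are collected and listed, so it can be, but no prespecified SAP analysis does so.

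**Conclusion.** The concern holds in limited form. The SAP has no analysis of secondary endpoint 14, specifies only a baseline-to-worst shift for laboratory data by arm, omits the protocol's by-visit laboratory summary, and declares neither omission. These are facts of the text and rest on no assumption.

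That the shift table hides most declines from a high baseline rests on the illustration: an assumed upper limit, assumed baselines and halving times, and a steady fall. The precision factors of about 1.46 to 1.77 are illustrative only, because the SDs are assumed and all 25 per arm are taken to contribute. They do not promise that a halving would be detected: at SD 1.2 with 25 per arm, power for a true halving at two-sided 0.10 is about 64%.

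The consequence is modest. No decision rule uses CRP and the primary analysis is unaffected. The SAP should still be corrected, because the endpoint is numbered, the data are already being collected and the remedy is cheap.

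**What to change.** 1. Add a CRP section to SAP 4.3.2, on the ITT population, with values and change from baseline by arm at Days 3, 8, 11, 15 and 29, and a between-arm estimate with 90% CI and descriptive p-value. Either of two models will do: the protocol 9.6 ANOVA with treatment and strata at each visit, or the repeated-measures model already written for viral load in SAP 4.3.2.9, applied to log CRP with log baseline CRP and with severity added, reported as a ratio of geometric means.
2. Restore the protocol 9.7 by-treatment, by-visit laboratory summary in SAP 4.5.3.
3. State in 4.5.3 whether *worst* includes baseline, and whether a baseline-to-last table is intended.
4. If the sponsor prefers not to analyse CRP or summarize laboratory data by visit, declare that in Section 5 with a reason.
5. Reconcile the laboratory days: SAP 1.2.6.3 reads "Hematology and chemistry laboratories on Days 1, 3, 5, 8, 11, 15 and 29", whereas the protocol and the SAP's own Table 1-1 have no Day 5.

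The cost is one SAP paragraph and one more table, with no new data. The small downside is that estimates at late visits will be less precise because data are sparser after discharge, and the repeated-measures model handles that only under missing at random.
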